## 10 Obligations of the Principal Investigator

## 10.1 Investigator Compliance

The Investigators must work according to standard ethical practice as laid down by their professional body and insert the product according to what is described in the handling procedures and the IfU for the products investigated in this clinical study. In addition, they must work in accordance with the "Declaration of Helsinki" (last revision Fortaleza 2013, WMA General Assembly, 2013), the ISO 14155:2011, the European Union's General Data Protection Regulation (GDPR) and with local legal and regulatory requirements.

The Investigators will ensure that the study is conducted in compliance with this protocol and the Clinical Study Agreement. Specifically, they are responsible for the informed consent process (Section 7.1.1).

# 11 Study Management

#### 11.1 Insurance

Only CE-marked products within their intended use are investigated. A patient insurance covering the complete duration of the study will be guaranteed by Straumann, if required by local regulations. A copy of the patient insurance will be provided by Straumann and filed in the ISF.

#### 11.2 Site Selection

All study sites were selected by a site qualification assessment where the study design and the study device was presented and the suitability of the sites confirmed (e.g., training and experience of the site staff, appropriate site equipment, access to EC, patient pool and expected recruitment period).

# 11.3 Regulatory and Ethical Requirements

#### 11.3.1 Informed Consent

Informed consent will be obtained from all patients prior to study participation as described in Section 7.1.1.

Patients who want to withdraw from the study will be offered an alternative treatment related to their dental condition. Patients will be advised of the need for the prescribed follow-up visits for their ongoing care, well-being, and collection of any safety data.

## 11.3.2 Study Registration

This protocol will be registered at clinicaltrials.gov at the study start.

#### 11.3.3 Ethics Committee

Prior to initiation of any study procedures, the protocol and informed consent form will be submitted to the local EC of investigators for review and approval before consenting can begin (7.1.1). In addition, any amendments to the protocol or informed consent will be reviewed and approved (if necessary) by the EC. The sponsor must receive a letter documenting the EC approval at the center prior to the initiation and/ or activation of the study. Any additional requirements imposed by the EC shall be followed.

The Investigator and/or Sponsor is responsible for reporting to EC (e.g., annual safety report, SAEs/SADEs, major protocol deviations) as required, during the course of the clinical study.

#### 11.3.4 Patient enrollment

Patient enrollment will only start after the sites have received the site activation letter from the sponsor.

## 11.3.5 Compliance

This study and any amendments will be performed according to International Organization for Standardization (ISO) 14155:2011 as far as applicable for post-market studies (any deviation will be documented in the internal review check based on Annex A of the ISO), local legal and regulatory requirements, and conform to the Declaration of Helsinki (last revision Fortaleza 2013).

## 11.3.6 Screening Failures

Any patient that has signed the Informed Consent Form and does not meet eligibility criteria at screening or re-evaluation at surgery is considered a screening failure. In the event of a screening failure, the eCRF should be completed up to the point (in V1 or V2) when the patient was determined to be a screening failure. The Study Termination eCRF page should also be completed. Screening failures will be replaced.

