# **6.3** Implant placement, sampling (baseline) (Visit 2, day 0)

The eligibility criteria need to be re-evaluated prior to implant placement to confirm eligibility. Straumann® BLT, Roxolid®, SLActive® and SLA® implants need to be placed in the assigned study quadrants as described in Section 3.3 (study treatment) and Section 0 (randomization) and recommendations given by the manufacturer. Blinding is applicable as described in section 0. **Note**: if there is no control and test implant available (one of each) that qualify as study implants (implant is assessed as primary stable (as defined in Section 7.2.3) at surgery, the abutment torque is at least 15 Ncm at surgery and the implant site fulfills the eligibility criteria, see Section 3.3 for further details), in 2 different quadrants, the patient needs to be **withdrawn** (see section 3.7.3).

Surgical procedure, implant placement, final abutment insertion and postoperative patient instructions are performed and documented as described in section 7.2.3.

The following evaluations will be performed and documented at this Visit, which are described in detail in **Section 7** 

- Review of the patient eligibility (inclusion and exclusion criteria)
- Randomization (before implant placement but after the preparation of the bed where the first implant will be placed, see Section 0 for further details)
- Documentation of surgical procedure and implant placement (see Section 7.2.3.)
- Periapical X-ray
- ISQ
- KM (buccal)
- AEs and device deficiencies
- Changes in concomitant medications and procedures
- Photographs of the implant site

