#### 7.2.1 Randomization

Assignment of one study test (placement of SLActive® implant(s)) and one study control quadrant(s) (placement of SLA® implant(s)) (=study quadrants) will be based on randomization at surgery visit, before implant placement but after the preparation of the bed where the first implant will be placed.

If there are two quadrants (suitable for study required implant placement) available in the same arch, those two quadrants will be selected for randomization. If this is applicable for the upper and lower arch the study site can select the arch for randomized. The randomization will be "left/right" to assign test/control treatment).

If the two available quadrants (suitable for study required implant placement) are from different arches the randomization will be "upper/ lower" to assign test/control treatment.

[figure not shown]

Randomization of eligible subjects will be performed using an Electronic Data Capturing (EDC) system. After log into the EDC system and entering the suitable quadrants for study required implant placement the system determines the treatment allocation. In case it's not possible to access the EDC system at site the Contract Research Organization (Factory) can provide the randomization arm.

The randomization in the EDC is programmed by Data Management. A block randomization process will be applied to randomize each center separately. Additionally, the randomization will be stratified for randomization in the same arch or in different arches, therein 2 randomization lists will be produced.

Quadrant I-IV are defined as:

The randomization code is a five digit number, consisting of the center number (e.g. 1 or 2), the individual patient number (01, 02, 03,...) and the randomization list number (01, 02). No access to the master randomization list will be available to the study centers, the external Monitors, the subjects and the Straumann non-Clinical-Research project team.

The study control and study test implant will be defined as described in Section 3.3

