# 8.4 Monitoring of Patients with Adverse Events

Any AE that occurs during the course of this study must be monitored and followed-up by the Investigator until one or more of the following have occurred:

- the AE is resolved,
- Pathological laboratory findings have returned to normal,
- steady state has been achieved, or
- it has been shown to be unrelated to the study devices.

The outcome of an event will be pursued until resolution or until the last data queries are issued following the patient's last study visit. For screening failures, ongoing AEs, ADEs and DDs must be followed and updated until the date the patient is deemed a screening failure. For patients documented as lost to follow-up, ongoing AEs, ADEs, and DDs will not be followed.

It is the responsibility of the sponsor to cooperate with the Investigator to assure that any necessary additional therapeutic measures and follow-up procedures are performed.

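### A patient can be declared a screening failure at the surgery visit with no cut-off before incision or randomisation, and follow-up of ongoing adverse events then stops that day

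*Combined protocol and SAP*

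**What the plan says.** Section 11.3.6 applies to any consented patient who "does not meet eligibility criteria at screening or re-evaluation at surgery is considered a screening failure". For such a patient "the eCRF should be completed up to the point (in V1 or V2) when the patient was determined to be a screening failure", and "The Study Termination eCRF page should also be completed". Replacement is unconditional: "Screening failures will be replaced".

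The timing of the surgical re-evaluation is set in section 6.3: "The eligibility criteria need to be re-evaluated prior to implant placement to confirm eligibility". Section 7.2.1 places randomisation "before implant placement but after the preparation of the bed where the first implant will be placed", and adds: "Randomization of eligible subjects will be performed using an Electronic Data Capturing (EDC) system".

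Section 8.4 sets a separate follow-up rule for this group: "For screening failures, ongoing AEs, ADEs and DDs must be followed and updated until the date the patient is deemed a screening failure".

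Section 3.7.3 separately obliges the investigator to withdraw a patient if control and test implants are not placed at Visit 2, or if there is no qualifying pair. Section 7.3.12 ends adverse-event collection when a patient withdraws or completes the final visit.

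**The concern.** The screening-failure label is meant for people who never entered treatment. Here it stays available inside the operation. If it is used after incision or drilling, the section 8.4 rule means that a complication still open at that moment has no recorded outcome, in a patient whose wound and prepared site result from the study procedure. Safety is one of the two co-primary hypotheses.

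There is also an accounting problem. Once the EDC has released an allocation, the patient has been randomised. The plan has no population or disposition line for such a patient if no implant follows, and two routes with different rules both fit the case.

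**Working it through.** The concern contains no figure, so the check is to set the provisions against each other.

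1. **The window.** The re-evaluation must precede implant placement (6.3). Preparation of the first bed and randomisation also precede implant placement (7.2.1). Sections 6.3, 7.1.3, 7.2.1 and 11.3.6 contain no sentence that closes the label before incision, drilling or allocation. Section 11.3.6 names Visit 2 expressly.

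2. **What can happen inside the window.** Device-deficiency collection begins at Visit 2 and covers instruments (7.3.13). Table 5 lists as an expected event that an implant cannot be placed. Bone volume and need for grafting are exclusion criteria (3.7.2). That either would first be judged inadequate during surgery is an assumption; the documents do not say so.

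3. **Two routes for one patient.** Take a patient found ineligible after the first bed is drilled, with no implants placed:

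| | Screening failure (11.3.6, 8.4) | Mandatory withdrawal (3.7.3) |
|---|---|---|
| Trigger | Eligibility not met at surgery | Control and test implants not placed at Visit 2 |
| Replacement | Always | Only while recruitment is open |
| Ongoing events | Followed to the date of the label | No special stop in 8.4; general rule |
| New events | eCRF completed only up to the failure | Collection ends at withdrawal (7.3.12), although 3.7.3 speaks of advising patients about visits that also serve safety data |
| Named in 9.1 counts | No | Yes, as withdrawals |

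   Both triggers are met, and no sentence gives one priority.

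4. **Where the patient is counted.** By the definitions in 9.3, the safety population needs receipt of a study device, ITT needs both implants and a follow-up measurement, and per-protocol needs one study implant of each kind. A patient with no implant is in none of them. Section 9.1 reports populations, withdrawals, subgroups and major deviations; it names neither screening failures nor all randomised patients. The patient does remain in the Screening and Enrollment Log as enrolled (3.7) and has a Study Termination page (11.3.6).

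5. **Side check on replacement.** The two routes replace differently, so I looked at power. Inputs from 9.4: SDs 0.20 and 0.22 mm, correlation 0, true difference 0.43 − 0.46 = −0.03 mm, margin 0.10 mm, one-sided alpha 0.05. SD of the difference = √(0.20² + 0.22²) = 0.2973 mm. With 51 pairs the noncentrality is 0.13 / (0.2973/√51) = 3.12, and the noncentral t gives 92.4%, the plan's own figure. If k patients are lost at surgery and not replaced (k is an assumption), the pairs left are (60 − k) × 0.80, rounded down: k = 0 gives 48 pairs and 91.0%; k = 3 gives 45 and 89.3%; k = 6 gives 43 and 88.0%. Power is therefore not a reason to keep the label open during surgery.

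**The case against.** The strongest reply is that the intended order is clear. The Visit 2 list in 6.3 puts the eligibility review ahead of randomisation, 7.2.1 randomises eligible subjects only, and suitable quadrants must be entered before the EDC allocates. A problem found while preparing the first bed comes before allocation, which leaves mainly the second site. Mandatory withdrawal already covers a patient who leaves surgery without both implants, with a recorded reason. The effect on the co-primary safety endpoint is also limited, because device relationship is assessed against study implants (8.2.2), which this patient does not have.

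Much of this stands. Labelling after allocation is permitted by a missing cut-off; it is not instructed. But eligibility before allocation is not eligibility before incision: the first bed is drilled before randomisation, so the safety gap remains even if the intended order is followed exactly. The withdrawal rule does not settle the matter either, because 11.3.6 claims the same patient on different terms.

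A reader might also infer from the mention of adverse device effects and device deficiencies in 8.4 that the protocol expects screening failures to have had surgery. That is not safe. The next sentence of 8.4 uses the same list for patients lost to follow-up, so it may be stock phrasing.

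**Conclusion.** The point holds as a gap in the rules, and it should be corrected. A stated rule ends follow-up of ongoing events on the date of a label that may be given after study surgery has begun. Status and replacement are contradictory between 11.3.6 and 3.7.3, and no all-randomised count is specified in section 9. Section 9.2 refers to a separate SAP for the detail of the effectiveness analysis; if that text specifies such a count, the last item falls away.

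Two stronger readings are tempting and are not supported:

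- **That these patients vanish from every count.** They stay logged as enrolled and have a Study Termination page, and anyone who received a study device meets the safety-population definition.
- **That an operator who knows the allocation can tilt the bone-level comparison towards SLActive.** This would need selective dropping by planned surface. The eligibility criteria do not depend on surface, and the documents give neither a frequency nor a size for it. A patient with no implants has no bone-level data and is outside the per-protocol analysis under any label, so relabelling makes the loss visible without changing the estimate.

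The number of patients affected cannot be estimated from the documents and may be small.

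**What to change.** - In 11.3.6 and 8.4, restrict screening-failure status to the period before the first incision at Visit 2.
- Class ineligibility found later as withdrawal or discontinuation at surgery under 3.7.3, with the reason recorded. If the EDC has released an allocation, count the patient as randomised.
- Follow that patient's adverse events and device deficiencies under the general rule of 8.4, and amend 7.3.12 so that collection does not stop on the operating day. The general rule is tied to the last study visit, so the sponsor should state the end point for a patient whose last visit is Visit 2.
- Reconcile 11.3.6 and 8.4 with 3.7.3 and 7.3.12 on status, replacement and follow-up, so that each patient fits one route.
- Add a disposition row in 9.1 for all randomised patients, showing those who left at surgery and why.

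The cost is a few sentences, one table row and some extra adverse-event contacts for patients without a study implant pair. If the 3.7.3 replacement rule is kept, a patient lost at surgery after recruitment closes is not replaced; the side check above shows that the loss of power is modest.

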#### 11.4 Protocol Deviations

Protocol deviations are to be avoided. Any deviation from the protocol may jeopardize the study outcome. Non-compliance of the patients, as well as of the Investigators, may lead to the closure of the respective study center.

#### 11.4.1 Definitions

A protocol deviation is any non-compliance with the clinical study protocol, IfU or associated documents. The non-compliance may be on the part of the patient, the Investigator or study staff. Protocol deviations are categorized as:

## a) Major protocol deviation:

- Increases risk to one or more participants;
- Adversely affects the safety, rights or welfare of one or more participants; or
- Adversely affects the integrity of the study.

Examples of major protocol deviations include: Informed consent obtained after the initiation of study procedures, failure to report a SAE, deviation from inclusion/exclusion criteria, deviation from withdrawal criteria (section 3.7.3), loading of the study control or study test implant not performed at the loading visit

b) Minor protocol deviation is a contravention of the protocol that does not impact participant's safety, nor compromises the integrity of the study data, neither/nor ethics of the study. Note: Several minor observations may collectively be considered as equal to a major protocol deviation.

Examples: Delay in performing study procedure (i.e., time window deviation).

Placement of study devices not according to randomization will be discussed on a case by case basis (e.g. assessment from the clinician of the clinical situation in the quadrant where the implants were placed compared to the randomized quadrant).

#### 11.4.2 Procedure

If a protocol deviation has occurred, the following procedure shall be followed:

- All deviations from the protocol must be recorded on the Protocol Deviation eCRF page.
- All major protocol deviations that occur at site shall be immediately notified to the sponsor and promptly reported to the local EC according to their requirements (see Section 11.3.3).
- **Minor protocol deviations** shall normally not be reported to the EC, but the sponsor should be notified as part of the study documentation.

Any documentation relating to protocol deviation will be filed in the Investigator Site File.

In case of prospective protocol deviation, the investigator shall notify the sponsor for agreement and submit to the EC for review and approval. The investigator should not implement any deviation from, or changes of, the protocol without agreement from the sponsor, and documented approval/favorable opinion of the EC, if applicable.

## 11.5 Record Management

## 11.5.1 Investigator Records

The following will be required from the Investigator prior to the initiation of the study:

- A signed Confidentiality Agreement (or equivalent statement in the Clinical Study Agreement)
- A signed copy of the Clinical Study Agreement with the sponsor
- Signed and dated curriculum vitae of the Investigator(s) and a copy of his/her dental license (if applicable)
- Signed financial disclosure of the Investigator(s), if applicable
- A signed copy of the final protocol and any amendments
- EC approval letter and EC approved informed consent document

#### 11.5.2 Source Documents

Source documents are defined as the original point of entry of a specific data point. Source documents will include, but are not limited to, progress notes, electronic data, computer

printouts, radiographs and recorded data from automated instruments. All source documents pertaining to this study will be maintained by the Investigator and made available for audit or inspection by authorized persons.

The following study specific data can be entered directly into the eCRF in this study:

- Pregnancy test information,
- Review of inclusion and exclusion criteria,
- Selection of quadrants for randomization,
- Pain relief (dose of Paracetamol),
- KM, PPD, BoP, soft tissue (Landry index),
- Final abutment torque,
- Bone level measurements
- Study specific questions in regard to: demographics, medical and dental history, documentation of surgery and documentation of final restoration.

## Source data used in this study:

## Study specific documentation

- eCRF
- Informed consent process, patient eligibility, study participation (patient files and/or screening and enrollment log)
- Defined study control and test implant (patient files)
- Study termination (patient files)
- Device disposal (implant position and article nr. of products used)
- Osseointegration, inflammation, bacterial load samples and readouts

#### Routinely collected but at defined study time points

- Patient questionnaire (OHIP-14)
- ISQ readout
- FMPS
- Photographs

# Routinely collected data during the daily practice

- Safety data (adverse events, device deficiencies, implant losses, prosthetic complication & failures
- Demographics
- Medical and dental history
- Concomitant medication and procedures
- Documentation of surgery and restoration

X-rays

# 11.5.3 Case Report Forms

Required clinical data for this study will be collected using an eCRF for all study patients from whom informed consent is obtained. Center numbers and subject ID will be used to track patient information throughout the conduct of the study.

The Principal Investigator or authorized designee is responsible for the timely and accurate completion of all eCRFs from source documents, query resolution and signature of all eCRFs. The Investigator will also allow Straumann representatives and/or regulatory bodies to review the data reported on the eCRF with the source documents as far as is permitted by local regulations.

## 11.5.4 Data Management

Data will be collected and recorded using a validated electronic data capturing (EDC) system provided to the centers prior to study start. Automatic queries will be built into the system prior to study start and throughout the project. The site should enter study data into the electronic database within 5 working days of a patient visit. Data capture will be source verified by the monitor and reviewed by the Data Manager. For any missing, inconsistent or illogical data, an electronic query will be generated and sent to the Investigator for completion. The Investigator answers the query, which will be documented.

Once all patients have completed the study, all queries are answered, and data were cleaned by data management, the database will be closed, and the statistical analysis will start.

Patient confidentiality will be strictly maintained.

Details of the data management procedures can be found in the Data Management Plan.

#### 11.5.5 Records/Data Retention

Original radiographs, photographs and study documents will be maintained at the study center in a file established for this study. All study documentation from the site needs to be stored at the study center according to local legal requirements following the completion of the study. The Investigator should have access to the study documents in order to answer any queries associated with the study. All other study records will be kept by Straumann once the study has been completed. These records will be maintained for 20 years at Straumann according to Straumann standard operating procedures.

